Study Co-ordinator	
Name: [name]
 
Address: Clinical Research Fellow, St. George's, University of London, Institute for Infection & Immunity, Paediatric Infectious Diseases Research Group, [name]
 
[contact]
 
Email: [contact]
 
[contact]

Sponsor	
St Georges, University of London
 
Name: [name]
 
Position: Research Governance and Facilitation Officer
 
Email: [contact]
 
Address: St George's Joint Research & Enterprise Services (JRES), St George's, University of London, [name]

Funder(s)	
Antibiotic Research UK
 
[name]
 
[name]
 
[name]
 
York
 
[name]

STUDY SUMMARY	
Study Title	Neonatal Antimicrobial Resistance and Outcome (neoAMRO)
Internal ref. no. (or short title)	neoAMRO
Study Design	
The neonIN surveillance network captures data on episodes of invasive neonatal infection on a web-based database (www.neonin.org.uk). Over 30 UK neonatal units currently contribute to this database in real-time. An episode of neonatal infection is defined as a positive culture collected from a normally sterile site such as the blood, cerebrospinal fluid (CSF) or urine (via catheter or suprapubic aspirate) for which clinicians prescribed at least five days of appropriate antibiotics. Clinical, demographic and microbiological data (including antimicrobial susceptibilities) are collected using a standardised online questionnaire, and denominator data regarding the total number of live-births and neonatal-admissions are collected for each neonatal unit.
 
For the purpose of this study, we will request information on the baby's status (alive/died/not known) at 28 days after the positive culture was obtained. If the baby is alive, then this baby becomes eligible as a control. If the baby has died, then further details will be sought including the date of death and whether death was attributed to the infection. Babies with positive cultures, who have died before receiving 5 days of appropriate antimicrobial therapy (currently a component of the surveillance case definition), will also be captured prospectively.

Study Participants	Infants on participating NNUs who have an episode of infection with a positive culture
Planned Size of Sample (if applicable)	Up to 800
Planned Study Period	Recruitment Period: June 2019 – 30 th September 2023 End of Study: 29th February 2024
Research Question/Aim(s)	
Primary aims
 
 • To identify the infections leading to death in babies on UK neonatal units. • To define the clinical characteristics of babies dying from infections. • To describe the management of babies dying from infections with a specific focus on their antimicrobial treatment and the antimicrobial resistance profiles of the causative organisms.
	
Secondary aims
 
In a case-control study to assess the hypothesis that babies who die from bacterial infections on neonatal units do so because they receive inappropriate antibiotic management.
 
To do this, babies who die from confirmed bacterial infections will be compared with babies who survive bacterial infections on a range of factors including appropriateness, dose and timeliness of antibiotic use.

FUNDING AND SUPPORT	
FUNDER(S)	FINANCIAL AND NON FINANCIAL SUPPORT GIVEN
Antibiotic Research UK (ANTRUK)	£4,000 over 36 months

ROLES AND RESPONSIBILITIES OF STUDY MANAGEMENT COMMITTEES/GROUPS & INDIVIDUALS

PROTOCOL CONTRIBUTORS

[name] and [name] (St. George's University of London) conceived the study; [name] and [name] initiated the study design and helped with implementation and will conduct primary statistical analysis. St. George's, University of London is the grant holder. All authors contributed to refinement of the study protocol and will approve the final manuscript.

STUDY TIMELINE

Key Objective	Measure of objective	Objective end point date
Application for modification of ethics permission for neonIN database	ethics approval	June 2018
Adaptation of on-line neonIN database	neonIN database adapted for new data	June 2018
Meeting of neonIN teams	meeting	July 2019
Set up of neoAMRO sites	preparation to start data collection	August 2019
On-line data collection commences	data entries	August 2019
Formal review of neonIN/neoAMRO data collection progress at 30 months	completeness of data, number of deaths recorded (>10)	February 2022
Formal review of neonIN/neoAMRO data collection at 36 months	completeness of data, number of deaths recorded (>40)	August 2022
neonIN /neoAMRO data collection completed at 49 months	completion of data entry	September 2023
analysis of all data and study report	study report completion	February 2024

ABBREVIATIONS	
AE	Adverse Event
AR	Adverse Reaction
BSI	Blood Stream Infection
CI	Chief Investigator
CRF	Case Report Form
GCP	Good Clinical Practice
GP	General Practitioner
GNB	Gram-Negative Bacteria
HCAI	Healthcare Associated Infection
HRA	Health Research Authority
ICF	Informed Consent Form
ICU	Intensive Care Unit
ISF	Investigator Site File
JRES	Joint Research and Enterprise Services
LOS	Late-Onset Sepsis
MARGNB	Multi-Resistant Gram-Negative Bacteria
NHS	National Health Service
NICU	Neonatal Intensive Care Unit
NIHR	National Institute for Health Research
NNU	Neonatal Unit
PI	Principal Investigator
PIDRG	Paediatric Infectious Diseases Research Group
REC	Research Ethics Committee
SAE	Serious Adverse Event
SCU	Special Care Unit
SGUL	St Georges, University of London
SGHFT	St Georges, University Hospitals NHS Foundation Trust
SOP	Standard Operating Procedure
TMF	Trial Master File

STUDY PROTOCOL

Neonatal Antimicrobial Resistance and Outcome (neoAMRO)

1 BACKGROUND

In 2011 we undertook a detailed analysis of death certificates over a 3 year period (England and Wales) and identified infection as the cause of 11% of neonatal deaths [1]. Where a pathogen was identified, 81% were bacterial, 11% were fungal and 9% were viral. The presentation of neonatal infection is non-specific therefore antimicrobial treatment is commenced before a causative organism is identified (called empiric therapy). The antimicrobial resistance patterns of the bacteria causing infections in our neonatal infection surveillance network (neonIN) show that there is a mismatch between recommended empiric antibiotics and the susceptibilities of relevant pathogens in a significant proportion (5-16%) [2,3]. The implication of these findings is that when the “wrong” empiric antibiotic combination is used to treat an infection the infant will be untreated until this is recognised and this may lead to a poor outcome, including death. For example, in a recent neonIN analysis of 118 episodes of Gram-negative neonatal infection, the 10 day attributable mortality was 18%, but this increased to 100% in those with strains resistant to gentamicin (a commonly used antibiotics in empiric regimens) (3/3) [4].

2 RATIONALE

Infections are an important cause of deaths in babies during their first weeks of life. Infection is typically non-specific in presentation. This means clinicians must start antibiotics early and “guess” which antibiotics to use. We know from our surveillance network that in 10-20% of cases the antibiotics chosen will not be the correct ones. A small study showed that when this mismatch occurred the babies had a high mortality. We wish to collect information on neonatal infections, identify the pathogens associated with deaths and determine if gaps in optimal antibiotic treatment are related or lead to poor outcomes.

3 THEORETICAL FRAMEWORK

Through our study we aim to understand and describe better those infections and risk factors that lead to death. The case-control study will enable us to determine if gaps in optimal management, such as the wrong antibiotic or the wrong dose, are associated with poor outcomes. We can then translate such information into practice and develop / improve clinical guidance in order to improve outcomes.

4 RESEARCH QUESTION/AIM(S)

4.1 Primary aims

- To identify the infections leading to death in babies on UK neonatal units.
- To define the clinical characteristics of babies dying from infections.
- To describe the management of babies dying from infections with a specific focus in their antimicrobial treatment and the antimicrobial resistance profiles of the relevant organisms.

4.2 Secondary aim

- In a case-control study we will assess the hypothesis that babies who die from bacterial infections on neonatal units do so because they receive inappropriate antibiotic management. To do this we will compare babies who die from bacterial infections with babies who survive bacterial infections on a range of factors including appropriateness, dose and timeliness of antibiotic use.

5 STUDY DESIGN and METHODS of DATA COLLECTION and DATA MANAGEMENT

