5.3 Data collection

Invasive infection episodes will be captured prospectively on a web-based infection surveillance database called neonIN (www.neonin.org.uk) which is coordinated by [name] at St George's University of London. The neonIN network currently includes 30 NNUs. For the purposes of this project all centres that wish to participate in neoAMRO will have access to the electronic data collection tool or web based database and will capture anonymised data regarding invasive episodes of infection.

For the purposes of the neoAMRO study, information on the baby's status at 28 days after the positive culture will be collected (alive / died / not known). If the baby is alive, then this baby becomes eligible as a control. However, if the baby has died, then further details will be sought including the date of death and whether the infection was believed to be associated with the baby's death. Babies with positive cultures but who have died before receiving 5 days of appropriate antimicrobial therapy (currently a component of the surveillance case definition), will also be captured prospectively.

Thus, the following data will be collected as part of the neoAMRO study:

- outcome at 28 days (alive / died / not known)
- date of death
- cause of death (if association with infection)
- antibiotics: name / start date / dose / frequency / stop date
- whether antibiotic regime was changed during therapy
- reason for change in antibiotic regime
- new antibiotics: name / start date / dose / frequency / stop date

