7.2 Sampling

7.2.1 Size of sample

Based on our previous data collection (see ref. 2), at the end of the enhanced study period we would expect to have data on up to 800 babies with invasive neonatal infections, approximately 50% will be due to coagulase negative staphylococci (CoNS), approximately 25% will be early onset sepsis and approximately 200 will be Gram-negative sepsis. Based on our recent data for case fatality rates (18% for Gram-negative bacteraemia, 8% for Group B streptococcus, 5% for staphylococcal aureus), we would expect around 50 deaths in this cohort.

All babies who have died within 28 days of a positive culture will then be compared with babies who have survived at 28 days across a range of relevant clinical and demographic factors. For all cases and for two controls per case (selected centrally, based on birth in same birthweight category and in same hospital), this will be performed through collection of anonymised data including birth gestation, birth weight and age at infection, antimicrobials administered for that infection episode (and if changed), relapses, length of stay and attributable mortality at 10 days using a standardised case report form. With approximately 50 cases of death and 100 controls, we anticipate that we will be able to explore the relationship between initial antimicrobial therapy and isolate susceptibility, with outcome, with great certainty. For example, with this sample size we can demonstrate a difference between susceptibility to empiric antibiotics of 80% among cases (or less) to 95% among controls, with 95% significance and 80% power; a difference that is clinically meaningful. A 10-day cut-off for attributable mortality will be used as early mortality is assumed to be more likely a direct consequence of infection than late mortality. Other risk factors for death will be assessed in univariate and multivariable logistic regression analyses.

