8.6 Data protection and patient confidentiality

All data should be handled in accordance with the Data Protection Act 2018 (UK implementation of the EU General Data Protection Regulation (GDPR)).

The participant's trial Identification Number (ID) only, will be used for identification. The Subject ID log can be used to cross reference participant's identifiable information and will be stored securely at participating sites.

1. Describe the nature of the processing:

A member of the neonatal team at each centre will be responsible for data collection and data input. As infection cases arise, they will be entered onto an electronic data collection tool or web based database. The central database will be anonymised with subjects identified only by neonIN study number, SEND/BADGER number and date of birth. Once age at infection has been calculated the DOB will be removed from the database. Each participating unit will hold its own secure database in order to link the infants' identifying data with study numbers. All data will be stored in compliance with the Data Protection Act.

2. Describe the scope of the processing:

Routine data collected: contributing hospital, DOB (for calculation of age at infection), gender, birth weight, gestation, ward type, date blood culture taken, pathogens isolates, whether the baby received

antibiotics 48 hrs before the culture was taken, whether the mother received antibiotics in the week before delivery, presence of intravenous or arterial lines catheters at time the culture sample was taken, clinical conditions associated with the infection, results of positive cultures including antibiogram, country of the participating unit, date of admission to the neonatal unit, number allocated to the baby on the SEND/Badger database, denominator data from each participating unit to demonstrate the unit activity (number of live births, number of admissions, patient days in NNU, central line days).

The following data to be collected in addition to the neonIN data, as part of the neoAMRO study : outcome at 28 days (alive / died / not known), date of death, cause of death (if association with infection), antibiotics: name / start date / dose / frequency / stop date, whether antibiotic regime was changed during therapy, reason for change in antibiotic regime, new antibiotics: name / start date / dose / frequency / stop date.

The data will be kept for 5 years post study termination/end.

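### The secondary aim puts a causal question about antibiotic management, but no organ-support or severity item at culture is listed, so its odds ratios are open to confounding in either direction

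*Protocol*

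**What the plan says.** Section 4.2 sets the hypothesis that "babies who die from bacterial infections on neonatal units do so because they receive inappropriate antibiotic management" and compares deaths with survivors "on a range of factors including appropriateness, dose and timeliness of antibiotic use". The Study Summary repeats it. Section 3 is more modest. It expects to learn whether "gaps in optimal management, such as the wrong antibiotic or the wrong dose, are associated with poor outcomes", and then intends to carry the result into clinical guidance. Section 5.1 confirms that the study is observational.

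Section 7.2.1 takes two controls per case, matched on birthweight category and hospital, giving about 50 deaths and 100 controls. Its open list of items for the case report form includes "birth gestation, birth weight and age at infection, antimicrobials administered for that infection episode (and if changed", and goes on to relapses, length of stay and 10-day attributable mortality. On analysis it says "Other risk factors for death will be assessed in univariate and multivariable logistic regression analyses" and names no covariates.

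The items that neoAMRO adds (section 5.3, repeated in section 8.6) are outcome at 28 days, date and cause of death, and treatment details: "antibiotics: name / start date / dose / frequency / stop date", with any change of regimen and the reason for it. The routine neonIN items in section 8.6 come closest to illness at culture: ward type, antibiotics in the 48 hours before the culture, and "presence of intravenous or arterial lines catheters at time the culture sample was taken, clinical conditions associated with the infection".

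**The concern.** Treatment here is chosen by clinicians, not assigned. A baby who looks very ill may be treated sooner, with a broader regimen or at a different dose, and is also more likely to die whatever is given. If the sickest babies are treated faster and more broadly, inappropriate management looks rarer among the deaths and a real harm is hidden. If they have had more earlier treatment and so carry more resistant organisms, the harm is inflated.

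Matching on birthweight category and hospital removes some differences between cases and controls, but not differences in acute illness at culture. Relapse and length of stay come after treatment and cannot stand in for baseline severity. What is at stake is the reading of the secondary result, since section 3 intends it to inform guidance.

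**Working it through.** **1. The plan's own figure.** Section 7.2.1 gives 80% power for susceptibility of 80% in cases v 95% in controls, with 50 cases and 100 controls. A two-sided 5% pooled normal test gives 78.7%, and 52 cases would be needed for 80%. The figure therefore reproduces. In terms of mismatch it is 20% v 5%, an odds ratio of (0.20/0.80)/(0.05/0.95) = 4.75. It is an unmatched, unadjusted power example and makes no allowance for confounding.

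**2. What the data could adjust for.**

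| Source | Items nearest to illness at culture |
|---|---|
| Section 5.3 (neoAMRO items) | none |
| Section 7.2.1 (case-control form, open list) | none named |
| Section 8.6 (routine neonIN items) | ward type (no time point); venous and arterial lines at culture (one combined item); associated clinical conditions (undefined); antibiotics in the previous 48 hours |

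None is an organ-support or severity item.

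**3. Illustration of size with no true antibiotic effect.**

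From the documents: 50 deaths in 800 babies (section 7.2.1), so the risk of death is 0.0625; overall mismatch of 10-20% (section 2).

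Assumed: 20% of babies severely ill at culture; severity odds ratio for death of 5 or 10; mismatch in severe v other babies of either 8% v 17% (overall 0.2 × 8 + 0.8 × 17 = 15.2%) or 25% v 12% (overall 14.6%).

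Solve for the baseline odds b so that 0.2 × bS/(1 + bS) + 0.8 × b/(1 + b) = 0.0625, where S is the severity odds ratio.

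- S = 5: risk of death 16.28% (severe) and 3.74% (other). Severe share is 52.1% of deaths and 17.9% of survivors.
- S = 10: risk of death 20.93% and 2.58%. Severe share is 0.2 × 0.2093/0.0625 = 67.0% of deaths and 0.2 × 0.7907/0.9375 = 16.9% of survivors.

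Mismatch in each group is the severe share times mismatch in the severe, plus the rest times mismatch in the others. For S = 10 with 8% v 17%:

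- deaths: 0.670 × 0.08 + 0.330 × 0.17 = 0.1097
- survivors: 0.169 × 0.08 + 0.831 × 0.17 = 0.1548
- crude odds ratio: (0.1097/0.8903)/(0.1548/0.8452) = 0.67

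| Mismatch, severe v other | S = 5 | S = 10 |
|---|---|---|
| 8% v 17% | 0.77 | 0.67 |
| 25% v 12% | 1.38 | 1.58 |

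The true odds ratio is 1 in every cell, so the departure from 1 is confounding alone.

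**4. The same model with a true odds ratio of 3.** The crude value is 2.21 (S = 5) or 1.82 (S = 10) for 8% v 17%, and 3.89 or 4.17 for 25% v 12%. Part of this shift is not confounding. With equal mismatch of 15% in both groups the crude value is already 2.83 or 2.64, because the odds ratio is non-collapsible. Step 3 is therefore the cleaner measure.

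**5. A harsher assumption.** Suppose 70% of cases and 10% of controls are severely ill, with mismatch of 25% in severe and 5% in other babies, and no true effect. Mismatch is 0.7 × 0.25 + 0.3 × 0.05 = 19% in cases and 0.1 × 0.25 + 0.9 × 0.05 = 7% in controls. The crude odds ratio is (0.19/0.81)/(0.07/0.93) = 3.12, still below the 4.75 of the power example.

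**The case against.** A reader might infer that the main antibiotic comparison is planned without adjustment. The protocol does not say so. The 80% v 95% contrast is introduced as a power example, and the sentence on other risk factors does not exclude the antibiotic exposure from the regression. Which covariates enter the model can properly be left to an analysis plan. A reader might also infer that the study cannot answer its question whatever the odds ratio. That goes too far: matching, regression and the routine proxies remove some confounding, and prior antibiotics over 48 hours bear directly on the inflation route.

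Other points also have force.

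- Empiric treatment starts before the organism is known (section 1), so mismatch depends partly on resistance that the prescriber cannot see. Confounding by illness is more plausible for timeliness and dose than for mismatch, yet the illustration models mismatch only.
- The illustration treats an unmatched cohort, and its severity inputs are assumptions.
- Neither the neonIN questionnaire nor the case report form is reproduced and the form's item list is open, so an unlisted severity field cannot be ruled out.
- Section 4.2 states a hypothesis to be assessed, not a conclusion.
- The aim is secondary; the descriptive primary aims are untouched.

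What survives is the data gap. An analysis plan can choose covariates but cannot supply ones that were not collected, and none of the three item lists names organ support or severity at culture. The causal wording of section 4.2 and the associational wording of section 3 are both protocol text and do not agree.

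**Conclusion.** The point holds in a limited form. The secondary aim frames a causal question, the matching does not address acute illness, and the listed data offer only partial proxies for it. The odds ratios for appropriateness, dose and timeliness are thus open to confounding whose direction the documents cannot settle. Under the inputs of step 3 in the working, a null effect of mismatch would appear as a crude odds ratio between 0.67 and 1.58. The range rests on the assumed prevalence of severe illness, its odds ratio for death and the two mismatch splits; it is an illustration, not an estimate of bias in this study. No stated figure in the protocol is wrong. The change is worth making but is not critical, and confidence is medium because the data collection forms are not shown.

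**What to change.** (a) In sections 5.3 and 7.2.1, add two yes/no items for cases and their matched controls, as charted at culture and before the first antibiotic dose of the episode: invasive ventilation and inotrope use. Later values should not be used, since they may be effects of treatment. Include the items in the model for the antibiotic exposures, for example as one combined organ-support indicator. Use the routine proxies only where they are confirmed to be recorded at culture: section 8.6 gives no time point for ward type and does not show that arterial lines are recorded separately.

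(b) In the Study Summary and section 4.2, restate the hypothesis as an association between inappropriate antibiotic management and death, in line with section 3.

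Cost: brief retrospective chart abstraction for about 150 babies (50 + 100) by the local teams, who already enter data retrospectively (sections 6 and 7.3.1), and one or two model degrees of freedom with about 50 cases. The rewording costs nothing except a weaker claim. Two binary items will not capture all of severity, so residual confounding should be acknowledged in the report.

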5.1 Study Design

This an observational study and no additional interventions will be performed

